3.4. End of Study

A subject is considered to have completed the study if he/she has completed all phases of the study, including the last study visit (ie, Safety Follow-Up [SFU] 2).

The end of the study is defined as the date of the last study visit of the last subject in the study globally.

4. STUDY POPULATION

4.1. Inclusion Criteria

Subjects must meet ALL of the following inclusion criteria to be eligible for enrollment into the study:

Key inclusion criteria

1. Men or women between ≥ 18 and ≤ 70 years of age at the time of informed consent
2. Moderate-to-severe AA as assessed by a SALT I score ≥ 25 and < 95 at Screening and Day 1/Baseline. Severity will also be confirmed by central review of photographs taken during Screening

3. Current episode of hair loss for ≥ 6 months but < 5 years
4. Stable disease condition (no significant growth of hair) in the last 6 months as assessed by the Investigator
5. Willing to keep the same hair style and color (eg, hair products, process, and timing for hair appointments) for the duration of the study

General inclusion criteria

6. Willing and able to comply with all clinic visits and study-related procedures and understand and complete study-related questionnaires
7. Provide signed informed consent prior to conducting any procedures
8. Females must meet either a or b of the following criteria and males must meet criterion c to qualify for the study:
 - a. Female who is not of childbearing potential by one of the following:
 - Postmenopausal, defined as no menses for 12 months without an alternative medical cause
 - Permanent sterilization procedure, such as hysterectomy, bilateral salpingectomy, or bilateral oophorectomy
 - b. Nonpregnant female of childbearing potential and agrees to using a highly effective contraception method during treatment and for 30 days following treatment that can achieve a failure rate of less than 1% per year when used consistently and correctly. The following are considered highly effective birth control methods:
 - Combined (estrogen and progestogen containing) hormonal contraception associated with inhibition of ovulation, which may be oral, intravaginal, or transdermal
 - Progestogen-only hormonal contraception associated with inhibition of ovulation, which may be oral, injected, or implanted
 - Intrauterine device (IUD)
 - Intrauterine hormone-releasing system
 - Bilateral tubal occlusion
 - Vasectomized partner, provided that partner is the sole sexual partner of the female of childbearing potential study participant and that the vasectomized partner has received medical assessment of the surgical success
 - Sexual abstinence (complete sexual abstinence defined as refraining from heterosexual intercourse for the entire period of risk associated with study drug). The reliability of sexual abstinence needs to be evaluated in relation to the duration of the clinical study and the preferred and usual lifestyle of the subject. Periodic abstinence (eg, calendar, symptothermal, post-ovulation methods) is not acceptable.

- c. Male with a pregnant or nonpregnant female of childbearing potential partner and agrees to using condoms during treatment and for 30 days following treatment

4.2. Exclusion Criteria

Subjects will be excluded from the study if they meet ANY of the following exclusion criteria:

Key exclusionary criteria

1. History of male or female pattern hair loss > Hamilton stage III or > Ludwig stage II
2. Other types of alopecia (eg, cicatricial/scarring alopecia [including central centrifugal cicatricial alopecia], traction alopecia, or telogen effluvium) or other diseases that could cause hair loss
3. Active scalp inflammation, scalp infection, scalp psoriasis, or any other scalp condition that may interfere with the SALT I assessment
4. Previous use of a Janus kinase (JAK) inhibitor (oral or topical), including participation in clinical studies of JAK inhibitors

Exclusionary criteria related to medications, therapies, or skin disease

5. Phototherapy on scalp within 4 weeks of Screening
6. Treatment with the following medications within 12 weeks of Screening:
 - a. Intralesional or systemic corticosteroids
 - b. Systemic glucocorticoids (inhaled or intranasal delivery are not exclusionary)
 - c. Immunoglobulin or blood products
7. Use of any biological agents (eg, dupilumab, adalimumab, ustekinumab, secukinumab) regardless of indication or systemic immunosuppressive/immunomodulating drugs (eg, cyclosporine, azathioprine, methotrexate) within 5 half-lives (if known) or 12 weeks before Screening, whichever is longer
8. Treatment with the following medications within 4 weeks of Screening:
 - a. Topical corticosteroids
 - b. Topical immunotherapy (eg, diphenylcyclopropenone, squaric acid)
 - c. Topical calcineurin inhibitors
 - d. Topical or oral minoxidil
9. Use of S1P receptor modulators (eg, fingolimod, siponimod, ozanimod, ponesimod), $\alpha 4\beta 1$ -integrin receptor antagonists (eg, natalizumab), and lymphocyte-depleting therapies (eg, rituximab, cyclophosphamide, bone marrow transplantation, total body irradiation) within 6 months before Screening or until lymphocyte count returns to normal, whichever is longer
10. History of or planned hair transplant procedure during the study
11. Planned microblading or micropigmentation of the scalp during the study
12. Received any investigational agent, including non-biologic agents and topical agents, within 5 half-lives (if known) or 4 weeks (whichever is longer) before Screening

13. Use of moderate/strong inducers or inhibitors that inhibit or induce at least two of the following: Cytochrome P450 (CYP) 2C8, CYP2C9, and CYP3A4 (eg, fluconazole, enzalutamide; [Table 4](#)) within 4 weeks before Screening.

Exclusionary criteria related to medical history

14. Known active bacterial, viral, fungal, mycobacterial infection, or other infection (including tuberculosis [TB] or atypical mycobacterial disease) or any major episode of infection that required hospitalization or treatment with intravenous antibiotics within 4 weeks before Screening or during Screening, or oral antibiotics within 2 weeks before Screening or during Screening. Superficial fungal infection of the nail bed is allowed
15. Have any of the following conditions or risk factors:
 - a. Primary or secondary immunodeficiency syndromes (eg, hereditary immunodeficiency syndrome, acquired immunodeficiency syndrome, drug-induced immune deficiency)
 - b. History of organ transplant (except corneal transplant)
 - c. History of an opportunistic infection (eg, *Pneumocystis jirovecii* pneumonia, cryptococcal meningitis, progressive multifocal leukoencephalopathy [PML])
 - d. History of disseminated herpes simplex or disseminated herpes zoster, or any episode of herpes zoster
 - e. Test positive for human immunodeficiency virus (HIV), hepatitis B virus (positive for hepatitis B surface antigen [HBsAg]), or active hepatitis C virus (HCV) (positive HCV antibody with detectable viral load) at Screening
 - f. History of active or latent TB (refer to [Appendix 3](#) for details of TB screening and interpretation of test results). The following is the EXCEPTION to the exclusion criterion:
 - Subjects with treated latent TB or latent TB diagnosed at Screening who have received ≥ 2 weeks of TB prophylaxis treatment prior to randomization, ruled out for active TB, and have not had recent close contact with a person with active TB. It is the responsibility of the Investigator to verify the adequacy of TB prophylaxis treatment and provide appropriate documentation. Note: The exception to the exclusion criterion outlined above does NOT apply to subjects residing in countries identified by the WHO as a high multi-drug resistance (MDR) TB burden country due to the risk of latent infection with MDR TB.
16. Received any live or live-attenuated vaccines within 4 weeks before Screening ([Section 6.9](#) offers additional details regarding vaccines)
17. History of malignancy of any organ system (other than localized squamous cell or basal cell carcinoma of the skin that have been excised or resolved), treated or untreated, within the past 5 years
18. Have any of the following conditions or receiving treatments that may affect cardiovascular function:
 - a. Myocardial infarction, unstable angina, stroke/transient ischemic attack, decompensated heart failure requiring hospitalization or Class III/IV heart failure within 8 weeks before Screening

- b. History or presence of second-degree or third-degree AV block, sick sinus syndrome, or periods of asystole for > 3 seconds without a functional pacemaker
 - c. Recurrent symptomatic bradycardia or recurrent cardiogenic syncope
 - d. Screening **OR** Baseline (Day 1) pre-randomization vital signs (taken in the sitting position) with an HR < 50 bpm, systolic blood pressure (BP) < 90 mm Hg, OR diastolic BP < 55 mm Hg. Vital signs may be repeated up to 3 times during a visit to confirm abnormal readings
 - e. Screening **OR** Baseline (Day 1) pre-randomization ECG with PR interval ≥ 200 ms or QT interval corrected using Fridericia's formula (QTcF) ≥ 450 ms in males or ≥ 470 ms in females
 - f. Start, stop, or change dosage of Class I-IV anti-arrhythmic drugs within 1 week of Screening
19. A history of or active diabetic retinopathy, uveitis, retinitis pigmentosum, or macular edema. Any recent intraocular surgery within 1 year of Screening
20. Active severe pulmonary disease (eg, chronic obstructive pulmonary disease or pulmonary fibrosis) or chronic pulmonary disease requiring intravenous corticosteroid treatment or hospitalization within 12 months before Screening or during the Screening Period
21. Have forced expiratory volume at 1 second (FEV₁) or forced vital capacity (FVC) < 70% of predicted values at Screening
22. Have any uncontrolled systemic disease(s) (eg, thyroid disorder, hypertension, diabetes). If the condition is considered controlled and the subject is on any medications (eg, thyroid medication or hormonal therapy) for treatment of diseases, the subject may be allowed to participate but must have been on a stable dose for at least 6 months prior to Screening and remain on a stable dose throughout the study.

Exclusionary criteria related to test or laboratory results (performed by central laboratory)

Note: A confirmed result means there have been 2 consecutive assessments showing a consistent abnormal, clinically relevant result.

- 23. Confirmed total white blood cell (WBC) count $\leq 3.5 \times 10^9$ cells/L OR absolute neutrophil count (ANC) $\leq 1.5 \times 10^9$ cells/L OR ALC < 1.0×10^9 cells/L at Screening
- 24. Confirmed estimated glomerular filtration rate < 30 mL/min/1.73 m² by the Chronic Kidney Disease Epidemiology Collaboration equation at Screening
- 25. Confirmed aspartate aminotransferase (AST) or alanine aminotransferase (ALT) > 2 \times upper limit of normal (ULN) and total bilirubin > 1.5 \times ULN (unless consistent with a history of Gilbert's Syndrome) at Screening

General exclusionary criteria

- 26. Lactating female who is breastfeeding
- 27. Any acute illness or medical condition including psychiatric disease, cognitive impairment, and alcohol/drug abuse/dependence, or signs/symptoms suspicious for a serious disease that, in the Investigator's opinion, could put the subject at increased risk for safety event(s), could interfere with participation in the study according to the study

protocol, or with the ability of the subject to cooperate and comply with the study procedures

Note: If a subject fails ≥ 1 Screening laboratory (or other) assessment criteria, the assessment(s) may be repeated once at the discretion of the Investigator, and the subject may be randomized if criteria are then met, provided the assessments are completed within the Screening Period. Any rescreening laboratory assessments beyond 1 time will need to be discussed with the Medical Monitor before proceeding.

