Subjects with certain cardiac risks, those with certain cardiac risks (eg, recent myocardial infarction, cardiac conduction delay, recurrent symptomatic bradycardia or syncope) will be excluded from the study. HR will be monitored closely via ECG and vital sign readings during the study, and direct observation will be performed at first dose (Double-Blind Treatment Period and Open-Label Extension Period) and on treatment re-initiation after a defined period of treatment interruption (refer to Section 10.5.7.4 for additional information on Day 1 monitoring). In addition to first-dose cardiac monitoring, continuous Holter monitoring (refer to Section 10.5.7.5) will be measured for 8 hours following dosing at Day 1 and Week 1 visits in the Double-Blind Treatment Period for Cohort 2, following dosing at Week 24 and Week 25 visits in the Open-Label Extension Period for Cohort 2, at the Week 24 visit and following transition from 2 mg to 3 mg in the Open-Label Extension Period for subjects in Cohort 1, and when a subject re-initiates study drug after a dosing interruption of a specified period (Section 6.3.2).

As additional safety measures, subjects with elevated liver enzymes, low lymphocyte counts, active severe pulmonary disease or a chronic pulmonary disease requiring intravenous

corticosteroid treatment or hospitalization, and active retinopathy or macular edema will be excluded from the study.

Further description of identified risks, any potential risks, and the Reference Safety Information (RSI) for etrasimod are provided in the current edition of the IB.

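### Exclusion criterion 25 joins the transaminase and bilirubin limits with *and*, so on the natural reading a confirmed isolated ALT/AST elevation meets no numeric exclusion, contrary to Protocol 1.2

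*Protocol*

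**What the plan says.** Criterion 25 in Protocol 4.2, repeated in the synopsis, is the only eligibility criterion with a transaminase limit. It names confirmed AST or ALT above 2 x "upper limit of normal (ULN) and total bilirubin" above 1.5 x ULN at Screening, with an exception where the finding fits a history of Gilbert's syndrome. The note above the laboratory criteria explains the qualifier: "A confirmed result means there have been 2 consecutive assessments showing a consistent abnormal, clinically relevant result".

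Protocol 1.2 lists, among the additional safety measures, that "subjects with elevated liver enzymes, low lymphocyte counts" and certain pulmonary and eye conditions will lead to exclusion. It mentions no bilirubin condition.

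Two lines above criterion 25, criterion 23 separates its blood-count limits with a capitalised OR, as in "OR absolute neutrophil count (ANC".

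**The concern.** If *and* is conjunctive, criterion 25 excludes only a subject whose transaminases and bilirubin are raised together. A subject with twice-confirmed high ALT and normal bilirubin would then pass every numeric criterion, however high the ALT. Section 1.2 tells ethics committees and investigators that such subjects are kept out.

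The stake is patient safety at entry and consistent application. SAP 5.5 expects approximately 29 sites, and two sites could reach opposite decisions on the same laboratory report. Entry could also be looser than continuation. Protocol 10.5.7.1 says stopping study drug should be considered at ALT or AST above 8 x ULN with no bilirubin condition, and a subject could be at that level before the first dose.

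**Working it through.** The plan states no figure on this point, so the check is one of logic and comparison.

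**1. Truth table for criterion 25.** Let A be confirmed AST or ALT above 2 x ULN. Let B be total bilirubin above 1.5 x ULN and not explained by Gilbert's. The joint reading excludes on A and B; the independent reading excludes on A or B. Values are multiples of ULN, and *eligible* means not excluded by criterion 25.

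| Screening profile | Joint reading | Independent reading |
|---|---|---|
| ALT 2.5, bilirubin 1.0 | eligible | excluded |
| ALT 6, bilirubin 1.0 | eligible | excluded |
| ALT 9, bilirubin 1.0 | eligible | excluded |
| ALT 1, bilirubin 2, no Gilbert's | eligible | excluded |
| ALT 1, bilirubin 2, Gilbert's | eligible | eligible |
| ALT 3, bilirubin 2, no Gilbert's | excluded | excluded |
| ALT 3, bilirubin 2, Gilbert's | eligible | excluded |

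The third row is at 9/2 = 4.5 times the criterion's own transaminase limit and above the 8 x ULN item in Protocol 10.5.7.1.

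**2. Is there another gate?** No other criterion in 4.2 gives an ALT or AST number. The Day 1 do-not-randomise list in 9.2.1 covers vital signs and ECG. The numeric extension criteria in 4.3 also cover only vital signs and ECG. Viral hepatitis (15e) and uncontrolled systemic disease (22) may catch some causes of a raised ALT. An otherwise unexplained elevation is left to the investigator's opinion under criterion 27.

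**3. How do the documents use AND for liver tests?** Protocol 10.5.7.1 has a combined item (ALT or AST above 3 x ULN AND bilirubin above 2 x ULN) alongside separate transaminase-only items. SAP 11.2 likewise tabulates ALT or AST above 3 x ULN AND bilirubin above 1.5 or 2 x ULN separately from transaminases alone. Sites used to this convention would read criterion 25 as joint.

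**4. What points to independent limits?** The other items in the Section 1.2 sentence each have a standalone criterion: lymphocytes in 23, pulmonary disease in 20, eye disease in 19. On the joint reading only liver enzymes do not. Criterion 23 shows how the same list writes limits that each exclude alone. The Gilbert's exception fits best where bilirubin alone can exclude; under the joint reading it readmits a Gilbert's subject whose ALT is also raised (last row).

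**The case against.** The strongest reply is that the joint criterion may be deliberate. The documents pair transaminases with bilirubin on purpose elsewhere, and the Gilbert's exception still has a function under the joint reading, because it stops benign bilirubin from completing the pair. This stands: intent cannot be settled from the text. It does not remove the conflict with Section 1.2, which would then need to change.

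Conversely, *and* can introduce the last item of a list, as in criterion 9, where any one of the drug classes excludes. On that reading there is no gap. But criterion 9 lists drug classes; for liver thresholds the documents' own usage is conjunctive.

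Section 1.2 is a summary with no threshold, and taken literally it would also cover values between 1 and 2 x ULN, which stay eligible under any reading of criterion 25. That is fair. It shows that Section 1.2 cannot set the limit, but not that isolated elevations of any size were meant to pass.

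The 9 x ULN example is extreme. A twice-confirmed, clinically relevant value of that size is an obvious candidate for criterion 27. Section 10.5.7.1 is on-treatment guidance, and Protocol 8.1 lists liver injury among reasons for which drug may, not must, be stopped. The example shows only that the text sets no ceiling; moderate elevations are the likelier case.

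A reader might infer that the gap applied to the whole trial. The documents do not support this: Cohort 1 enrolled under earlier protocol versions that are not available, and eligibility is known to have changed between versions (SALT I limits in Protocol 10.3.1, episode duration in SAP 3.1). A reader might also infer that liver toxicity on treatment would be missed. It would not: Protocol 10.5.4 requires review of each laboratory report and repeat testing of clinically significant values, and the 10.5.7.1 triggers and the SAP 11.2 table are multiples of ULN that do not depend on Baseline.

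**Conclusion.** The point holds as a wording defect in a safety criterion, with moderate confidence. On the reading that sites are most likely to apply, criterion 25 leaves a confirmed isolated ALT/AST elevation without a numeric exclusion and does not deliver what Section 1.2 states. Independent limits were probably intended, but that is an inference.

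The visible text is known to govern Cohort 2, about 42 subjects. How many would have an isolated elevation is unknown: the documents give no frequency, and the answer could be none. The consequence is confined to eligibility and consistency between sites. Sample size, power, alpha and the efficacy analyses do not depend on it. It should be fixed because the correction is small and concerns patient safety.

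**What to change.** In Protocol 4.2 and in the synopsis, restate criterion 25 as two independent limits at Screening: confirmed AST or ALT above 2 x ULN, OR confirmed total bilirubin above 1.5 x ULN, with the Gilbert's exception attached to bilirubin only. Repeating *confirmed* avoids a new doubt about the bilirubin limit. The essential change is that the transaminase limit stands alone. The bilirubin-alone exclusion goes beyond what Section 1.2 says, and the sponsor should confirm that it is wanted. If the sponsor did intend the joint criterion, leave criterion 25 and reword Section 1.2 to describe it.

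In either case, have the Medical Monitor review the central-laboratory screening liver values already held for randomised subjects.

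The cost is a short text change in two places of an amendment, a review of existing data, and a few more screen failures, some of them for isolated bilirubin not due to Gilbert's. No new procedure is needed, and subjects between 1 and 2 x ULN with bilirubin within its limit stay eligible under this criterion.

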4.3. Exclusion Criteria (for the Open-Label Extension Period)

Subjects will be excluded from the Open-Label Extension Period if they meet the following exclusion criteria at the Week 24 visit:

1. Week 24 predose vital signs (taken in the sitting position) with an HR < 50 bpm, systolic BP < 90 mm Hg, OR diastolic BP < 55 mm Hg. Vital signs may be repeated up to 3 times during the visit to confirm abnormal readings.
2. Confirmed predose Week 24 ECG with PR interval ≥ 200 ms or QT interval corrected using QTcF ≥ 450 ms in males or ≥ 470 ms in females. Presence on Week 24 ECG of second-degree or third-degree AV block, sick sinus syndrome, or periods of asystole for > 3 seconds without a functional pacemaker.
3. The Investigator considers the subject to be unsuitable for any reason to participate in the Open-Label Extension study.

Note: If a subject fails to enter the Open-Label Extension Period due to Exclusion Criterion 1 or 2, the assessment may be repeated once at the discretion of the Investigator, and the subject may be dosed if the criterion is then met, provided the assessment is completed within the Week 24 visit window. Any repeated vital sign assessments beyond 1 time will need to be discussed with the Medical Monitor before proceeding.

5. SUBJECT RESTRICTIONS

For dosing requirements, including holding the dose prior to the study visit on study visit days, refer to Dosage and Administration, Section 6.3. Prohibited medications/procedures are located in Section 6.8.2.

Subjects are expected to continue their usual scalp care routine without notable changes for the course of the treatment periods and follow-up period. Subjects are prohibited from using tanning booths and sunbathing, and from shaving their scalp 2 weeks prior to visits.

Subjects are to keep the same hair style and color for the duration of the study.

6. STUDY DRUG

6.1. Study Drug(s) Administered

Study drug(s) in this study include the investigational medicinal product(s), defined as a pharmaceutical form of the active substance being tested (test product) and the placebo being used as a reference (reference therapy). Study drug(s) are listed in [Table 1](#).

Table 1: Study Drugs

Study Drug	Dose	Mode of Administration	Frequency	Formulation
Etrasimod	2 mg	Oral	Once daily	Tablet
Etrasimod	3 mg	Oral	Once daily	Tablet
Placebo	Not applicable	Oral	Once daily	Tablet

6.2. Identity of Study Drugs

6.2.1. Etrasimod

The active pharmaceutical ingredient in etrasimod tablets is APD334 L-arginine (the L-arginine salt of (*R*)-2-(7-(4-cyclopentyl-3-(trifluoromethyl)benzyloxy)-1,2,3,4-tetrahydrocyclopenta[*b*]-indol-3-yl)acetic acid), which is an off-white to light-brown solid with an aqueous solubility of approximately 1.38 mg/mL at pH = 8.9 and 30°C. APD334 L-arginine is manufactured, packaged, tested, and released in compliance with cGMP.

Etrasimod tablet drug product is a blue, round, biconvex, plain, immediate-release, film-coated tablet. Etrasimod tablets are composed of APD334 L-arginine active pharmaceutical ingredient and excipients (microcrystalline cellulose, mannitol, sodium starch glycolate, magnesium stearate, and Opadry® II blue 85F90951) and is supplied in the dosage strength (based on etrasimod free-acid content) of 1 mg and 2 mg.

